7.2.5 Investigator Responsibility for Reporting Adverse Events

All Adverse Events will be reported to the Ethical Committee of Hospital del Mar and investigators in accordance with all applicable global laws and regulations, i.e., per ICH Topic E6 (R1) Guidelines for Good Clinical Practice.

8.0 STATISTICAL ANALYSIS PLAN

8.1 Statistical Analysis Plan Summary

Linear mixed-effects models will be used to test the association between treatment arm and all primary and secondary endpoints. These models will include an outcome measure as the dependent variable, treatment assignment, time of measurement, and their interaction as independent variables and a random intercept for participant and site to account for the longitudinal and clustered nature of the data. If imbalances exist in baseline characteristics between treatment groups, sensitivity analyses will be conducted by including the covariate in the mixed-effects models as an independent variable to determine the impact it may have on the desired association. For the primary outcome, the interaction between treatment assignment and the 6 weeks follow-up will be assessed, with statistical significance indicating a difference in the change in 9-HPT is present between treatment groups at V5. All other time points and outcome measures will be treated as secondary. These analyses will be conducted following the intention to treat principle. Additional exploratory analyses will be conducted on the per protocol population defined as those who completed at least 70% of therapeutic sessions.

Table 4 Statistical analysis plan

Study Design Overview	Transcutaneous Electrical Spinal Stimulation (tSCS) for Improving Upper Limb Function in People with MS
Treatment Assignment	Active stimulation: tSCS Sham: stimulations using a non-active electric stimulation
Analysis Populations	Intention to treat Per Protocol
Primary Endpoint(s)	Differences in the nine-hole peg test (9-HPT) affected hand in the tSCS treated vs. sham groups by the end of treatment (V3 vs V5)
Key Secondary Endpoints	1. Percentage of responders: 20% difference on the 9HPTd (minimal clinically important difference (MCID)) from baseline to end of the study 2. Change in the 9HPT dominant and non-dominant hand from baseline to end of the study 3. Change in the Action Research Arm Test (ARAT) from baseline to end of the study 4. Change in the modified Ashworth Scale (mAS) for spasticity assessment from baseline to end of the study

	
5. Hand strength measured by Grip and Pinch force dynamometers (Figure 10)
 
6. Change in the NeuroQOL Upper Extremity function from baseline to end of the study
 
7. Change in the Modified Fatigue Impact Scale (MFIS) from baseline to end of the study
 
8. Change in Global Impression of change (GIC) from baseline to end of the study

Exploratory endpoints	
Statistical Methods for Key Efficacy Analyses	Linear mixed-effects models will be used to test the association between treatment arm and all primary and secondary endpoints.
Statistical Methods for Key Safety Analyses	Descriptive statistics
Interim Analyses	No interim analysis for efficacy or safety is planned for this study.
Multiplicity	Not planned
Sample Size and Power	
Sample size: n=60
 
For a large, standardized effect size (Cohen's $d=0.8$), with a sample size of 52 (26 in each arm) we would have greater than 80% power to detect a significant difference in 9HPT between treatment arms using a two-sample t-test and a two-sided significance level of 0.05. Assuming a common standard deviation of 5.5, this corresponds to a difference of 4.4 units between treatment groups. Allowing for a conservative attrition rate of 15% (our previous trial in SCI with a similar design had 10% attrition⁴⁻⁶), we plan on enrolling 60 participants.
 
Furthermore, as our proposed analysis is a linear mixed-effects model, we anticipate greater efficiency resulting in a slightly higher power. Reimbursement of travel expenses will be used to promote retention.

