Measurements & Procedures	
 1. tSCS 2. Occupational Therapy 3. Clinical scales and PROs
Study Product / Intervention	tSCS is a non-invasive electric stimulation system that has shown good tolerability and signs of efficacy for improving UL disability
Controls	Sham (fictitious stimulation) will be used as control arm
Number of Participants & Rationale	
N=60 (30:30)
 
Rationale: accepting an alpha risk of 0.05 and a beta risk of 0.1 in a two-sided test, 10 subjects are necessary in each group to recognize as statistically significant a minimum difference of 10 units on the 9HPT scale between any pair of groups assuming that 2 groups exist. The common deviation is assumed to be 5.5. It has been anticipated a drop-out rate of 10%.

Study Duration:	
24 months
 
6 months recruitment, 9 months randomized phase, 6 months OLE, 3-month analysis and clinical scientific report

Timelines:	
 ● First Patient First Visit (FPFV): January 1st, 2025 ● Last Patient Last Visit (LPLV): December 30th 2026
Study Schedule:	
Patients in Spain are recruited from the three MS centers (Hospital del Mar, Hospital Clínic and Hospital Sant Pau) in Barcelona and treated in a single therapy center at Hospital del Mar located closely to all of them. Patients in the Netherlands are recruited at the Rijndam center, Erasmus Medical Center.
 
Run-in period (6 weeks with occupational therapy)
 
Double-Blinded period: 6 weeks for safety and efficacy assessments

	Open Label Extension (6 weeks) for safety and durability of efficacy
Study Center:	Hospital del Mar (HMar); Hospital Clinic of Barcelona (HCB); Hospital Sant Pau (HSP), all in Barcelona, Spain; Rijndam center, Erasmus Medical Center (EMC)
Statistical Analysis Plan	
The primary and secondary endpoints will be assessed using linear mixed-effects models (LME). These models will include the outcome measure as the dependent variable, and treatment group, time, and their interaction as independent variables, with random intercepts for participant and site to account for the longitudinal and clustered nature of the data.
 
Populations : 1) Intention to treat population; 2) Per protocol population: patients that completed 70% of the therapeutic sessions

A list of abbreviations used in this document can be found in Appendix 12.3.

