5.3 Randomization

Treatment allocation/randomization will occur centrally using an interactive voice response system / integrated web response system (IVRS/IWRS). There are 2 treatment arms: stim and sham. Subjects will be assigned randomly in a 1:1 ratio to either tSCS or sham.

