8.9 Sample Size and Power Calculations

Sample size

Sample size: n=60

Power for the primary hypothesis

For a large, standardized effect size (Cohen's $d=0.8$), with a sample size of 52 (26 in each arm) we would have greater than 80% power to detect a significant difference in 9HPT between treatment arms using a two-sample t-test and a two-sided significance level of 0.05. Assuming a common standard deviation of 5.5, this corresponds to a difference of 4.4 units between treatment groups. Allowing for a conservative attrition rate of 15% (our previous trial in SCI with a similar design had 10% attrition⁴⁻⁶), we plan on enrolling 60 participants. Furthermore, as our proposed analysis is a linear mixed-effects model, we anticipate greater efficiency resulting in a slightly higher power. Reimbursement of travel expenses will be used to promote retention.

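### The primary mixed model does not use baseline 9HPT to gain precision; a common baseline mean or a baseline covariate would improve it at almost no cost

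*Protocol*

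**What the plan says.** Section 8.1 of the protocol specifies the primary analysis: "These models will include an outcome measure as the dependent variable, treatment assignment, time of measurement, and their interaction as independent variables". Random intercepts for participant and site complete the model, and the synopsis (Section 1.0) repeats the fixed effects as "treatment group, time, and their interaction as independent variables". The primary test is the treatment-by-time interaction at 6 weeks, read as a between-arm difference in the change in 9HPT at V5. Covariates enter only in a sensitivity analysis, if a baseline imbalance is seen, and then as an additional independent variable.

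Section 5.3 states: "Subjects will be assigned randomly in a 1:1 ratio to either tSCS or sham". Section 8.9 sizes the trial "using a two-sample t-test and a two-sided significance level of 0.05", and says of the standardised effect of 0.8 that "we would have greater than 80% power to detect a significant difference in 9HPT". It adds: "Assuming a common standard deviation of 5.5, this corresponds to a difference of 4.4 units between treatment groups". It then says that "as our proposed analysis is a linear mixed-effects model, we anticipate greater efficiency resulting in a slightly higher power".

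**The concern.** Randomisation makes the two arms' pre-treatment means equal in expectation. A model with a treatment main effect still estimates them separately. The treatment contrast then subtracts the whole baseline difference, whereas the best linear use of baseline subtracts only the fraction rho of it. Given an observed baseline difference D between arms, the change contrast is off by -(1-rho) x D. This averages to zero over randomisations, but it adds variance.

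At stake is precision. About 26 evaluable patients per arm give power only just above 80%, and a measurement already scheduled at the randomisation visit could narrow the interval without any new data.

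**Working it through.** **Inputs.** From Section 8.9: d = 0.8, SD 5.5, 26 per arm, two-sided alpha 0.05. From Section 8.1: the model. The correlation rho between baseline and V5 9HPT is not in the protocol, so a range of 0.5 to 0.9 is assumed. Section 8.9 does not say whether 5.5 is the SD of a single score or of change.

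**The plan's own figure.** 0.8 x 5.5 = 4.4 units. The noncentral t with 50 df and noncentrality 0.8 x sqrt(26/2) gives 80.7% power (82.2% by the normal approximation). The stated figure reproduces.

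**What the planned contrast estimates.** Random-intercept models were fitted to simulated complete data (26 per arm, three visits, time as a category). One data set was generated at each rho:

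| Quantity | rho 0.5 | rho 0.8 |
|---|---|---|
| Planned model, treatment x last visit | -4.4644 (SE 1.533) | -3.8399 (SE 0.960) |
| Difference in mean change | -4.4644 | -3.8399 |
| Planned model plus baseline as main effect | -4.4644 (SE 1.533) | -3.8399 (SE 0.960) |
| Common baseline mean | -4.5522 (SE 1.276) | -3.4574 (SE 0.880) |

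The second row equals the first, so the planned contrast is the difference in mean change. The third row also equals the first: a covariate that is constant over time, entered as a main effect, leaves the interaction where it was. The fourth row has the smaller standard error.

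**Variance.** In units of the single-score variance, and with equal variances at both visits, the change contrast has variance proportional to 2(1-rho) and the baseline-adjusted contrast to 1-rho^2. The ratio is (1-rho^2)/[2(1-rho)] = (1+rho)/2. In 4,000 simulated trials per value, the ratio was 0.78, 0.86 and 0.96 at rho 0.5, 0.7 and 0.9, against 0.75, 0.85 and 0.95 from the formula.

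**Power if 5.5 is the SD of change** (26 per arm, effective d = 0.8/sqrt((1+rho)/2)):

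| rho | Variance ratio | Effective d | Power |
|---|---|---|---|
| planned | 1 | 0.80 | 80.7% |
| 0.5 | 0.75 | 0.924 | 90.4% |
| 0.7 | 0.85 | 0.868 | 86.6% |
| 0.9 | 0.95 | 0.821 | 82.7% |

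**Link to baseline spread.** With a change SD of 5.5 and equal variances, rho = 1 - 5.5^2/(2 x SD^2). No baseline SD is given, so these values are assumed:

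| Baseline SD (s) | rho | Power with adjustment |
|---|---|---|
| 5.5 | 0.50 | 90.4% |
| 10 | 0.85 | 83.7% |
| 15 | 0.93 | 82.1% |
| 20 | 0.96 | 81.5% |
| 30 | 0.98 | 81.1% |

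**If 5.5 is the SD of a single score**, the planned contrast has 80.7% power at rho 0.5 and 95.5% at rho 0.7. With baseline adjustment these become 90.4% and 97.7%.

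**The case against.** The planned contrast is unbiased under randomisation, and it answers the question that Section 8.1 poses, a difference in change. Section 8.4.1 also commits to change from baseline. A reader might infer that the primary analysis is biased or invalid. It is neither, and this objection stands in full.

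A reader might also infer that a gain of about ten power points is being lost. That needs rho near 0.5, which under the change-SD reading means a baseline SD of about 5.5 s. Section 5.1.2 admits patients from 33.3 to 240 s. A wide spread with a fixed change SD pushes rho up and shrinks the gain to a few points or less. This also stands.

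A third tempting inference is that the efficiency sentence in Section 8.9 is false. The protocol does not support that. A likelihood-based mixed model can use partial records that a completers' t-test drops. Pooling residual variance over visits adds degrees of freedom: at d = 0.8, 100 df gives 81.5% against 80.7% at 50 df. If 5.5 is a single-score SD, the planned contrast also beats a t-test on V5 values whenever rho exceeds 0.5. The sentence can therefore be true, but it does not say where the gain comes from.

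Finally, a common baseline mean is safe only at a visit before stimulation. The endpoint in Section 8.4.1 takes V3 as its reference, while the flow chart (Section 6.0) and Section 7.1.5.1.2 place randomisation and the first stimulation at Visit 2. Constraining the arms to be equal after stimulation has begun could introduce bias. The objection is right that this must be settled first.

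**Conclusion.** This is an improvement in precision at almost no cost; it does not correct a bias. As written, the primary contrast makes no efficient use of baseline 9HPT, and the imbalance sensitivity analysis would not recover the loss. On complete data it would return the same estimate, which could be misread as evidence that an imbalance had no effect.

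The variance saving is 5% to 25% for an assumed rho of 0.9 to 0.5. If 5.5 is the SD of change, this is worth about 2 to 10 power points over that range, and about 0 to 3 points if the baseline SD is 10 to 30 s. The algebra is firm for complete data with categorical time, and approximate when visits are missing. The size is uncertain because neither rho nor the meaning of 5.5 is stated. A reader might conclude that the trial is underpowered. The documents do not show that: the stated power reproduces, and a shortfall would need a single-score SD of 5.5 together with rho below 0.5, for which the protocol gives no evidence.

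**What to change.** 1. Reconcile the baseline visit (V3 in the endpoint against randomisation and first stimulation at Visit 2), and define baseline as the last 9HPT before the first stimulation.
2. In Section 8.1 and the synopsis, replace the fixed effects by time plus treatment x post-baseline time, with one common baseline mean. Alternatively, model only the post-baseline values, with baseline 9HPT (and its interaction with time) as a covariate. Keep the random intercepts.
3. Do the same for the continuous secondary scales that have a baseline.
4. In Section 8.9, state whether 5.5 is the SD of change or of a single score, and attribute the expected efficiency gain to baseline adjustment and the use of partial records.

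The cost is wording and at most about one degree of freedom, with no new data or visits. The change should be made before unblinding so that the adjustment is not chosen after the fact.

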5.4 Stratification

Randomization will be stratified by center.

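### The participant random intercept imposes equal correlation between all visits, so the validity of the primary 9HPT test depends on which visits are modelled, and the protocol does not say which

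*Protocol*

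**What the plan says.** Protocol section 8.1 specifies a linear mixed model with treatment, time and their interaction, and "a random intercept for participant and site to account for the longitudinal and clustered nature of the data". Section 1.0 repeats the structure: "with random intercepts for participant and site to account for the longitudinal and clustered nature of the data". Neither section mentions a random slope, a residual correlation or an unstructured matrix.

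For the primary outcome, section 8.1 says that "the interaction between treatment assignment and the 6 weeks follow-up will be assessed". The endpoint is the 9HPT difference "in the tSCS treated vs. sham groups by the end of treatment (V3 vs V5"). Section 8.1 then adds: "All other time points and outcome measures will be treated as secondary". It does not say whether those other time points enter the same model as the primary contrast.

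The flow chart in section 6.0 schedules the 9HPT on Days 42, 61 and 84 in the double-blind period and on Day 126 in the open-label extension. Under section 2.1, sham participants are offered active tSCS in that extension, while the active group is followed without further stimulation or therapy.

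**The concern.** A participant random intercept with independent residuals is compound symmetry. The model pools a single residual variance over all modelled visits and applies it to every change between visits. Measurements taken closer together usually correlate more strongly, so short-gap changes vary less than long-gap changes. The primary contrast spans 42 days. The other gaps in the double-blind period are 19 days (Day 42 to 61) and 23 days (Day 61 to 84). Pooling them with the 42-day gap would understate the variance of the primary contrast.

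The point estimate is not at risk. With complete data it is the difference in mean change whichever covariance is used. The standard error, confidence interval and p-value of the one primary test are at risk.

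**Working it through.** **Inputs from the protocol.** 26 evaluable participants per arm and two-sided 0.05 (section 8.9); 9HPT on Days 42, 61, 84 and 126 (section 6.0); random intercepts only (section 8.1). I take V5 to be Day 84. This is inferred from the 6-week follow-up and the flow chart, because no table maps visit numbers to days one by one.

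**Assumed.** The correlation between visits decays exponentially with the gap. The protocol gives no correlation, so a range is shown.

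**The plan's own figure.** 26 per arm at d = 0.8 gives power of 80.7% by the noncentral t, and 0.8 × 5.5 = 4.4. Both agree with section 8.9. That calculation uses a two-sample t-test, so it says nothing about the covariance structure.

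**Formula.** With complete data and equal variances σ² at each visit, the random-intercept residual variance estimates σ²(1 − r̄), where r̄ is the mean of all pairwise correlations. With n per arm:

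- model SE² = 4σ²(1 − r̄)/n
- true SE² = 4σ²(1 − r₄₂,₈₄)/n
- SE ratio = √[(1 − r̄)/(1 − r₄₂,₈₄)]
- type I error ≈ 2[1 − Φ(1.96 × ratio)]

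**Worked case, 42-day correlation 0.8, Days 42/61/84.** r(42,61) = 0.8^(19/42) = 0.904; r(61,84) = 0.8^(23/42) = 0.885; r(42,84) = 0.800. So r̄ = 2.589/3 = 0.863. Ratio = √(0.137/0.200) = 0.828. Type I error = 2[1 − Φ(1.62)] ≈ 10.5%.

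**Same case with Day 126 added.** The extra correlations are 0.640 (42–126), 0.708 (61–126) and 0.800 (84–126). So r̄ = 4.737/6 = 0.7895. Ratio = √(0.2105/0.200) = 1.026, slightly conservative.

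**Range by visits modelled (no measurement noise, 42-day correlation 0.25 to 0.90).**

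| Visits in model | SE ratio | Type I error |
|---|---|---|
| 42, 84 | 1.00 | 5% |
| 42, 61, 84 | 0.82 to 0.88 | 8.4 to 10.7% |
| 42, 61, 84, 126 | 0.98 to 1.04 | 4.2 to 5.5% |

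**Measurement noise, Days 42/61/84.** A noise share w multiplies every correlation by (1 − w), which moves the structure towards equal correlation. For a decaying part with 42-day correlation 0.7 to 0.9:

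| Noise share | SE ratio | Type I error |
|---|---|---|
| 0 | 0.82 to 0.83 | 10.2 to 10.7% |
| 10% | 0.88 to 0.92 | 7.1 to 8.4% |
| 20% | 0.91 to 0.95 | 6.2 to 7.3% |
| 30% | 0.94 to 0.97 | 5.8 to 6.7% |

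**Simulation check.** In 20,000 trials per setting with 26 per arm and Days 42/61/84, the random-intercept test rejected in 10.0%, 10.7% and 10.6% of null trials at 42-day correlations of 0.7, 0.8 and 0.9. In the same trials the unstructured analysis, which with complete data is the comparison of change scores, rejected in 4.9 to 5.1%.

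**Does the site intercept matter here?** It is constant within a participant, so it cancels from a change contrast. With 60 participants at four sites (assumed participant SD 15, residual SD 4), the exact SE of the interaction is 1.4639 at every site variance from 0 to 1600. With 15% missing at Day 84 it moves from 1.54596 to 1.54607, under 0.01%. Fitted models with and without the site term gave the same estimate (2.6728) and SE (1.466).

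**The case against.** The strongest reply is that the protocol does not commit itself to the model in which the test is wrong. The endpoint names two visits, and a two-visit model has no error. A model of all scheduled visits, Day 126 included, has almost none. The 10 to 11% figure also needs correlation that decays purely with time and no measurement noise, which is unlikely for a timed manual test. Finally, section 8.1 is a summary, and a SAP could still add a residual covariance.

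Most of this stands as a limit on size. The error is conditional, and the upper end is not a forecast. It does not remove the point. Treating other time points as secondary reads most naturally as a time factor with several levels. The random intercepts are also given as the means of handling the longitudinal correlation, so a SAP that followed the text would inherit the problem. Day 126 is no safeguard either. It restores the error rate only because a longer gap happens to offset the shorter ones, and it does so with data collected after the arms have changed treatment.

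A reader might also infer that the primary standard error rests on a site variance estimated from few centres: "Patients in Spain are recruited from the three MS centers", a fourth is in the Netherlands, and "Randomization will be stratified by center". The inference fails, because the site intercept cancels from this contrast. An estimated site variance of zero would leave the primary result unchanged, and making centre a fixed effect would not materially alter it.

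**Conclusion.** The point holds in conditional form. With Days 42, 61 and 84 modelled and decaying correlation, the primary standard error is about 8 to 18% too small at noise shares of 0 to 10%, and about 3 to 9% too small at 20 to 30%. The nominal 5% test then runs at about 6 to 11%. If equal correlation truly held across visits, there would be no distortion. The correlations, the noise shares and the reading of V5 as Day 84 are assumptions.

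The documents do not support saying that the primary test is inflated as planned. They support saying that its validity depends on which visits are pooled, that this is not stated, and that the stated covariance makes an assumption which a trial with three double-blind visits and about 52 evaluable participants does not need. A better model is available at almost no cost, so the text should be changed.

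**What to change.** In sections 8.1 and 1.0, state that the primary model uses the double-blind visits only (Days 42, 61 and 84), with an unstructured within-participant covariance in place of the participant intercept and Kenward-Roger degrees of freedom. The primary contrast stays the treatment-by-time interaction at Day 84. Analyse Day 126 separately, because by then sham participants may have received active tSCS.

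The cost is analysis wording only. Three visits need six covariance parameters instead of two (participant and residual variance). With 26 per arm, the degrees of freedom for the contrast fall from 2 × 25 × 2 = 100 to about 2 × 25 = 50. This raises the critical value from about 1.98 to 2.01. No change to the site term is needed on this account.
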